3.4.3.2 De Novo Subjects

Subjects will be excluded if they meet any of the exclusion criteria in Table 3.4.3.2-1.

| Tab | le 3.4.3.2-1 Exclusion Criteria for De Novo Subjects |
|-----|---|
| 1. | Females who are breast-feeding and/or who have a positive pregnancy test result prior to receiving IMP. |
| 2. | Sexually active males or FOCBP who do not agree to practice 2 different methods of birth control or remain abstinent during the course of the trial and for 30 days after the last dose of IMP for female subjects, and 90 days after the last dose of IMP for male subjects and their partners who are FOCBP. Unless the subject is sterile (ie, females who have had a bilateral oophorectomy or hysterectomy or who have been postmenopausal for at least 12 consecutive months; or males who have had a bilateral orchidectomy) or remains abstinent, 2 of the following precautions must be used: vasectomy, tubal ligation, vaginal diaphragm, intrauterine device, birth control pills, birth control injection, birth control implant, birth control patch, condom with spermicide, or sponge with spermicide. Male subjects who do not agree to refrain from donating sperm from screening through 90 days after the last dose of IMP. |
| 3. | Subjects with DSM-5 diagnosis of Other Specified or Unspecified Attention-Deficit/Hyperactivity Disorder as confirmed by ACDS Version 1.2. |
| 4. | Subjects with life-time history of electroconvulsive therapy, or a life-time history of vagal nerve stimulation or deep brain stimulation for the treatment of depression. |
| 5. | Subjects with current comorbid psychiatric disorder that either could be expected to require treatment with medications prohibited in this trial, or to confound efficacy or safety assessments. Examples include, but are not limited to, psychotic disorder (current or lifetime), bipolar disorder (current or lifetime), generalized anxiety disorder, obsessive-compulsive disorder, panic disorder, a current major depressive episode, or posttraumatic stress disorder, as established by the MINI. |
| 6. | Subjects with a clinically significant current DSM-5 diagnosis of borderline, antisocial, paranoid, schizoid, schizotypal, histrionic, narcissistic, avoidant, or dependent personality disorders. |
| 7. | Subjects who meet the following criteria for "Baseline/Screening" version of the C-SSRS: Suicidal Ideation Items 4 or 5 within the last 6 months OR 5 C-SSRS Suicidal Behavior Items (actual attempt, interrupted attempt, aborted attempt, preparatory acts, or behavior) AND Whose most recent episode meeting criteria for any of these 5 C-SSRS Suicidal Behavior Items occurred within the last 2 years |
| | OR |
| 8. | Subject has any medical or psychological condition(s) or state(s) that in the investigator's opinion would prohibit the subject from completing the trial or would go against the subject's best interest with his/her participation in the trial. This would include any significant illness or unstable medical condition that could lead to difficulty complying with the protocol. |
| 9. | Subject has a history of epilepsy, seizures (other than infantile febrile seizures), syncope, Tourette's Disorder, serious neurological disease, history of significant head trauma with clinically significant loss of consciousness, dementia, cerebrovascular disease, Parkinson's disease, or intracranial lesions. |
| 10. | Subject has a life-time history of a pattern of abuse or diversion of stimulants. |
| 11. | Subjects with any current or suspected drug or alcohol use disorder or have met the DSM-5 criteria for a substance use disorder in the past 6 months. Nicotine use disorder is not exclusionary. |

Confidential - Proprietary Information

| Tab | le 3.4.3.2-1 Exclusion Criteria for De Novo Subjects |
|-----|--|
| 12. | Subjects that have a positive alcohol test (via breathalyzer or blood), a positive drug screen for cocaine, or other illicit drugs (excluding marijuana). Subjects with a positive drug screen for confirmed prescription or OTC use of ADHD medications at screening will be required to undergo a washout period (Section 4). NOTE: Subjects that test positive for marijuana may be permitted to be enrolled if they have no evidence of a substance use disorder, and if they agree to refrain from use for the duration of the trial. Allowance for subjects testing positive for marijuana at screening require explicit approval from the medical monitor. |
| 13. | Subjects with known intellectual disability (intellectual developmental disorder), including mild |
| | adaptive functioning impairment, or clinical evidence of intellectual disability based on the opinion of the investigator. |

| | NOTE: In addition, subjects should be excluded if they have any other abnormal laboratory tests, vital sign results, or ECG findings which in the investigator's judgment are medically significant and that would impact the safety of the subject or the interpretation of the trial results. Tests with abnormal results should be repeated to ensure reproducibility of the abnormality before excluding a subject based on the criteria noted above. |
| 18. | Subjects with hypothyroidism or hyperthyroidism (unless condition has been stabilized with |
| | medications for at least the past 90 days) or an abnormal result for free T ₄ at screening (free T ₄ is measured only if result for TSH is abnormal). |
| · | |

Confidential - Proprietary Information

38

| Tab | le 3.4.3.2-1 Exclusion Criteria for De Novo Subjects |
|-----|--|
| 19. | Subjects receiving any of the prohibited medications within the specified period prior to the first dose of trial medication or who would be likely to require prohibited concomitant therapy during the trial (Section 4). |
| 20. | Subjects with a history of prior exposure to centanafadine. |
| 21. | Subjects with a history of dermatologic adverse reactions or anaphylaxis secondary to drug exposure. |
| 22. | Subjects with HIV seropositive status/acquired immunodeficiency syndrome, seropositive status for hepatitis B (ie, HBsAg positive), or hepatitis C (ie, anti-HCV positive and HCV RNA positive). |
| 23. | Subjects who have previously been enrolled in this trial and subsequently withdrawn. |
| 24. | Subject has participated in a clinical trial involving either an investigational medication or a non-medication intervention within the last 60 days prior to screening or has participated in more than 2 clinical trials involving either an investigational medication or non-medication intervention within the past year. |
| 25. | Any subject who, in the opinion of the investigator, should not participate in the trial. |

See Section 3.9 for details regarding screen failures.

Nonchildbearing potential is defined as male and female subjects who are surgically sterile (ie, male subjects who have undergone bilateral orchidectomy and female subjects who have undergone bilateral oophorectomy or hysterectomy) and female subjects who have been postmenopausal for at least 12 consecutive months.

Subjects must agree to restrictions to medications and lifestyle as described in Section 4.

3.5 Endpoints

3.5.1 Primary Endpoint

The primary endpoint in this trial is the long-term safety and tolerability of centanafadine SR tablets administered BID (400 mg TDD), as assessed by the frequency and severity of treatment-emergent adverse events (TEAEs).

3.5.2 Secondary Endpoints

None.

3.5.3 Exploratory Endpoint(s)

Exploratory efficacy endpoints for the open-label treatment period are as follows:

- Change from baseline in Adult ADHD Investigator Symptom Rating Scale (AISRS) Total Score, by trial visit and at the last visit (ie, Week 52/ET);
- Change from baseline Clinical Global Impression-Severity of Illness Scale (CGI-S), by trial visit and at the last visit (ie, Week 52/ET);
- Change from baseline in ADHD Impact Module Adult (AIM-A) Score by trial visit and at the last visit;

3.5.4 Additional Safety Endpoints

Additional safety variables will include clinically significant changes in: clinical laboratory tests (hematology, serum chemistry, coagulation parameters, and urinalysis), physical examinations, vital sign measurements, and electrocardiograms (ECGs).

The Columbia-Suicide Severity Rating Scale (C-SSRS) will be used to assess and classify reported suicidal behavior. By-subject listings of physical examination findings will be reviewed as a further assessment of safety.

Assessments of withdrawal symptoms will be performed using Study Medication Withdrawal Questionnaire (SMWQ).

Abuse-related AEs and AEs involving medication irregularities will be recorded verbatim on source documentation with detailed narratives (Section 5.5).

3.6 Measures to Minimize/Avoid Bias

Not applicable; this is an open-label trial.

3.7 Trial Procedures

Individual participation for rollover subjects who complete the trial without early withdrawal will be approximately 54 weeks, consisting of a 52-week open-label treatment period, and 10-day safety follow-up period after the last dose of IMP. Individual participation for de novo subjects who complete the trial without early withdrawal will be approximately 58 weeks, consisting of a screening period of up to 28 days, a 52-week open-label treatment period, and a 10-day safety follow-up after the last dose of IMP.

Trial assessment time points are summarized in Table 3.7-1 and Table 3.7-2 (rollover subjects from Trial 405-201-00013 or Trial 405-201-00014) and Table 3.7-3 and Table 3.7-4 (de novo subjects).

In addition to the trial assessment time points summarized (Table 3.7-1 and Table 3.7-2 for rollover subjects and Table 3.7-3 and Table 3.7-4 for de novo subjects CCI

Confidential - Proprietary Information

41

| Table 3.7-1 | Schedule of Assessme Baseline Through En | ents - Rol d of Trea | llover Subject atment | s from [| Frial 405 | 5-201-00 | 013 or 🛛 | Frial 40 | 5-201-000 | 14 - | | |
|-----------------------------------|---|-------------------------------------|--------------------------|--------------|--------------|--------------|--------------|--------------|---------------------------|---------------------|--|--|
| | Baseline | 52-Week Open-label Treatment Period | | | | | | | | | | |
| | 7-day follow-up visit from Trial 405-201-00013 or | W1& | | | | | | | | End of Treatment | | |
| | Trial 405-201-00014/ Baseline for | 2 (± 3 | W 4, 8, 12 & 16 | W 20 (± 3 | W 26 (± 3 | W 32 (± 3 | W 38 (± 3 | W 44 (± 3 | W 48 ^b (± 3 | W 52/ET | | |
| | Trial 405-201-00015 ^a | days) | (± 3 days) | days) | days) | days) | days) | days) | days) | (± 3 days) | | |
| Visit | 1 | 2 & 3 | 4, 5, 6, & 7 | 8 | 9 | 10 | 11 | 12 | 13 | 14 | | |
| ENTRANCE/HISTORY | Y | | | | | | | | | | | |
| Informed consent | Х | | | | | | | | | | | |
| Inclusion/exclusion criteria | Х | | | | | | | | | | | |
| Concomitant medication(s) | X ^c | Х | Х | Х | Х | Х | Х | Х | Х | Х | | |
| HIV/HBsAg/ anti-HCV | Х | | | | | | | | | | | |
| Urine pregnancy test ^d | Х | Х | Х | Х | Х | Х | Х | Х | | Х | | |
| SAFETY | | | · | • | • | | • | | | • | | |
| Adverse events | X ^c | Х | Х | Х | Х | Х | Х | Х | X | Х | | |
| Physical examination | X ^e | | Xf | | Х | | | | | Х | | |
| Vital signs | X ^c | Х | Х | Х | X | Х | Х | Х | | Х | | |
| 12-lead ECG | Х | X | X ^g | L | X | L | Х |] |] | Х | | |

Confidential - Proprietary Information

Version 4.0, 02 Jun 2020

Until the information herein is released by Otsuka to the public domain, the contents of this document are Otsuka confidential information and should not be duplicated or re-distributed without prior written consent of Otsuka.

| Table 3.7-1 | Schedule of Assessments - Rollover Subjects from Trial 405-201-00013 or Trial 405-201-00014 - | | | | | | | | | | |
|---|---|-----------------|------------------------|-----------------|-----------------|-----------------|-----------------|-----------------|-----------------|------------------------|--|
| | Baseline Through En | d of Trea | atment | | | | | | | | |
| | Baseline | | | 52-W | eek Open | -label Tr | eatment I | Period | | | |
| | 7-day follow-up visit from Trial 405-201-00013 or Trial 405-201-00014/ | W 1 & | W 4 9 12 9 | W 20 | Wac | W 22 | W 20 | XV 44 | W 49b | End of Treatment | |
| | Baseline for | | W 4, 8, 12 & | W 20 | W 26 | W 32 | W 38 | ₩ 44 | ₩ 40 (+ 2 | W 52/FT | |
| | Trial 405-201-00015 ^a | (± 3) davs) | $(\pm 3 \text{ days})$ | (± 3) davs) | $(\pm 3 \text{ days})$ | |
| Visit | 1 | 2 & 3 | 4, 5, 6, & 7 | 8 | 9 | 10 | 11 | 12 | 13 | 14 | |
| Clinical laboratory tests (hematology, serum chemistry [including HbA1c and TSH], and urinalysis) | X | | X ^f | | Х | | X | | | Х | |
| PT/INR | Х | | | | Х | | | | | Х | |
| SMWQ | | | | | | | | | | Х | |
| Urine drug screen | X ^c | | X ^h | | Х | | | | | Х | |
| Alcohol testing ⁱ | X ^c | | X ^h | | Х | | | | | Х | |
| C-SSRS | X ^c | Х | Х | Х | Х | Х | Х | Х | | Х | |
| EFFICACY | | | | | | | | | | | |
| AISRS | X ^c | Х | X | Х | Х | Х | Х | Х | | Х | |
| CGI-S | Х | Х | Х | Х | Х | Х | Х | Х | | Х | |
| AIM-A | Х | | | | Х | | | | | Х | |
| | | | | | | | | | | | |

Confidential - Proprietary Information

Version 4.0, 02 Jun 2020

Until the information herein is released by Otsuka to the public domain, the contents of this document are Otsuka confidential information and should not be duplicated or re-distributed without prior written consent of Otsuka.

| Table 3.7-1 | Table 3.7-1 Schedule of Assessments - Rollover Subjects from Trial 405-201-00013 or Trial 405-201-00014 - Baseline Through End of Treatment | | | | | | | | | | | |
|-------------------------------|---|--|--------------|-------|-------|-------|-------|-------|-------------------|---------------------|--|--|
| | Baseline | Baseline 52-Week Open-label Treatment Period | | | | | | | | | | |
| | 7-day follow-up visit from Trial 405-201-00013 or | W 1 & | | | | | | | | End of Treatment | | |
| | Trial 405-201-00014/ | 2 | W 4, 8, 12 & | W 20 | W 26 | W 32 | W 38 | W 44 | W 48 ^b | | | |
| | Baseline for | (± 3 | 16 | (± 3 | (± 3 | (± 3 | (± 3 | (± 3 | (± 3 | W 52/ET | | |
| | Trial 405-201-00015 ^a | days) | (± 3 days) | days) | days) | days) | days) | days) | days) | (± 3 days) | | |
| Visit | 1 | 2 & 3 | 4, 5, 6, & 7 | 8 | 9 | 10 | 11 | 12 | 13 | 14 | | |
| OTHER | | | | | | | | | | | | |
| IMP dispensing | Х | Х | Х | Х | Х | Х | Х | Х | | | | |
| IMP return and accountability | | Х | Х | Х | Х | X | Х | Х | | Х | | |

AIM-A = ADHD Impact Module – Adult; AISRS = Adult ADHD Investigator Rating Scale; C-SSRS = Columbia-Suicide Severity Rating Scale; ECG=electrocardiogram; PT/INR = prothrombin time/international normalized ratio; W = week.

^aDosing will commence the day after the baseline visit.

^bTelephone, web, or other acceptable means of contact.

^cAssessments may be conducted at the 7-day follow-up visits of Trial 405-201-00013 or Trial 405-201-00014, and the information can be carried over into Trial 405-201-00015 for the baseline visit.

^dIf the urine pregnancy test is positive, the result will be confirmed with a serum pregnancy test.

^ePhysical examination at baseline will include height measurements.

^fWeek 8 only.

^gWeeks, 4, 8, and 16 only.

^hWeeks 4 and 12 only.

¹Alcohol testing may be conducted via a blood test or using a breathalyzer.

CCI CCI

Confidential - Proprietary Information

| Table 3.7-2Schedule of Assessments - RFollow-up | ollover Subjects from | n Trial 40: | 5-201-00013 | 3 or Trial 4 | 05-201-00014 | - |
|---|--|--|---|---|---|--|
| Period | | | Follow- | up ^a | | |
| | 1 (+1) days after the last dose of IMP | 2 (+1) days after the last dose of IMP | 3 (+ 1) days after the last dose of IMP | 5 (+ 1) days after the last dose of IMP | 7 (+ 2) days after the last dose of IMP | 10 (+ 2) days after the last dose of IMP |
| Visit | 15 | 16 | 17 | 18 | 19 | 20 |
| ENTRANCE/HISTORY | | | | | | |
| Concomitant medication(s) | Х | Х | Х | Х | Х | Х |
| EFFICACY | | | | | | |
| AISRS | | Х | | | Х | |
| SAFETY | | | | | | |
| Adverse events | Х | Х | Х | Х | Х | Х |
| Vital signs | | Х | | | Х | |
| SMWQ | Х | Х | Х | Х | Х | Х |
| Urine drug screen | | Х | | | Х | |
| Alcohol testing ^b | | Х | | | X | |
| C-SSRS | | X | | | Х | |

^aFollow-up telephone calls will be conducted at 1, 3, and 5 days after the last dose of IMP, in-clinic visits on 2 and 7 days after the last dose of IMP, and a follow-up telephone call [or web, or other acceptable means of contact] 10 days after the last dose of IMP).

^bAlcohol testing may be conducted via a blood test or using a breathalyzer.

| Table 3.7-3 | Schedule of | Assessme | nts - De N | ovo Subjects | - Baseli | ne Thro | ugh End | l of Trea | tment | | | |
|--|------------------------|-----------------------|------------|-------------------------------------|----------|---------|---------|--------------|--------------|-------------------|--------------------------------|--|
| | | | | 52-Week Open-label Treatment Period | | | | | | | | |
| | | | W1&2 | W 4, 8, 12, & 16 | W 20 | W 26 | W 32 | W 38 (+ 3 | W 44 (+ 3 | W 48 ^c | End of Treatment W 52/ET | |
| | Screening ^a | Baseline ^b | days) | $(\pm 3 \text{ days})$ | days) | days) | days) | days) | days) | days) | $(\pm 3 \text{ days})$ | |
| Visit | 1 | 2 | 3 & 4 | 5, 6, 7, & 8 | 9 | 10 | 11 | 12 | 13 | 14 | 15 | |
| ENTRANCE/HISTORY | | | | | | | | | | | | |
| Informed consent | Х | | | | | | | | | | | |
| Inclusion/exclusion criteria | Х | Х | | | | | | | | | | |
| Demography | Х | | | | | | | | | | | |
| Concomitant medication(s) | Х | Х | Х | Х | Х | Х | Х | Х | Х | Х | Х | |
| Medical history | Х | | | | | | | | | | | |
| ACDS | X | | | | | | | | | | | |
| Identification of comorbidities using MINI | Х | | | | | | | | | | | |
| Psychiatric history | Х | | | | | | | | | | | |
| HIV/HBsAg/ anti-HCV | Х | | | | | | | | | | | |
| Urine pregnancy test ^d | Х | Х | Х | Х | Х | Х | Х | Х | Х | | Х | |
| SAFETY | • | | • | | • | • | • | • | • | | • | |
| Adverse events | Х | Х | Х | Х | Х | Х | Х | Х | Х | Х | Х | |
| Physical examination | X ^e | Х | | X ^f | | X | | | | | Х | |
| Vital signs | Х | Х | Х | Х | Х | Х | Х | X | Х | | Х | |
| 12-lead ECG | X | Х | Х | X ^g | | Х | | Х | | | Х | |

Confidential - Proprietary Information

Version 4.0, 02 Jun 2020

Until the information herein is released by Otsuka to the public domain, the contents of this document are Otsuka confidential information and should not be duplicated or re-distributed without prior written consent of Otsuka.

| Table 3.7-3 | Schedule of | chedule of Assessments - De Novo Subjects - Baseline Through End of Treatment | | | | | | | | | |
|--|------------------------|---|--------------------------|-----------------------------------|-----------------------|-----------------------|-----------------------|------------------------------|-----------------------|--|--|
| | | | | | 52-We | ek Open- | label Trea | tment Pe | riod | | |
| | Screening ^a | Baseline ^b | W 1 & 2 (± 3 days) | W 4, 8, 12, & 16 (± 3 days) | W 20 (± 3 days) | W 26 (± 3 days) | W 32 (± 3 days) | W 38 (± 3 days) | W 44 (± 3 days) | W 48^c (± 3 days) | End of Treatment W 52/ET (± 3 days) |
| Visit | 1 | 2 | 3 & 4 | 5, 6, 7, & 8 | 9 | 10 | 11 | 12 | 13 | 14 | 15 |
| Clinical laboratory tests (hematology, serum chemistry [including HbA1c and TSH], and urinalysis) | Х | х | | X ^f | | X | | Х | | | X |
| PT/INR | | Х | | | | Х | | | | | Х |
| SMWQ | | | | | | | | | | | Х |
| Urine drug screen | Х | Х | | X ^h | | Х | | | | | Х |
| Alcohol testing ⁱ | Х | Х | | X ^h | | Х | | | | | Х |
| C-SSRS | Х | Х | Х | Х | Х | Х | Х | Х | Х | | Х |
| EFFICACY | | | | | | | | | | | |
| AISRS | | Х | Х | Х | Х | Х | Х | Х | Х | | Х |
| CGI-S | | Х | Х | Х | Х | Х | Х | Х | Х | | Х |
| AIM-A | | Х | | | | Х | | | | | X |
| | | | | | | | | | | | |

Confidential - Proprietary Information

Version 4.0, 02 Jun 2020

Until the information herein is released by Otsuka to the public domain, the contents of this document are Otsuka confidential information and should not be duplicated or re-distributed without prior written consent of Otsuka.

| Table 3.7-3 | Table 3.7-3 Schedule of Assessments - De Novo Subjects - Baseline Through End of Treatment | | | | | | | | | | | |
|-------------------------------|--|-----------------------|---------|-------------------------------------|-------|-------|-------|-------|-------|-------------------|---------------------|--|
| | | | | 52-Week Open-label Treatment Period | | | | | | | | |
| | | | W 1 & 2 | W 4, 8, 12, | W 20 | W 26 | W 32 | W 38 | W 44 | W 48 ^c | End of Treatment | |
| | _ | | (± 3 | & 16 | (± 3 | (± 3 | (± 3 | (± 3 | (± 3 | (± 3 | W 52/ET | |
| | Screening ^a | Baseline ^D | days) | (± 3 days) | days) | days) | days) | days) | days) | days) | (± 3 days) | |
| Visit | 1 | 2 | 3 & 4 | 5, 6, 7, & 8 | 9 | 10 | 11 | 12 | 13 | 14 | 15 | |
| OTHER | · | | • | | | • | | | | | | |
| IMP dispensing | | Х | Х | Х | Х | Х | Х | Х | Х | | | |
| IMP return and accountability | | | Х | Х | X | X | X | Х | Х | | Х | |
| CCI | | | | | | | | | | | | |

^aScreening will include a washout period that can range from 7 to 28 days.

^bDosing will commence the day after the Baseline visit.

^cTelephone, web, or other acceptable means of contact.

^dIf the urine pregnancy test is positive, the result will be confirmed with a serum pregnancy test.

^ePhysical examination at screening will include height measurements.

^fWeek 8 only.

^gWeeks 4, 8, and 16 only.

^hWeeks 4 and 12 only.

ⁱAlcohol testing may be conducted via a blood test or using a breathalyzer.

CCI

Confidential - Proprietary Information

Version 4.0, 02 Jun 2020

| Table 3.7-4 Schedule of Assessments - De Novo Subjects - Follow-up | | | | | | |
|--|--|--|---|---|---|--|
| Period | Follow-up ^a | | | | | |
| | 1 (+1) days after the last dose of IMP | 2 (+1) days after the last dose of IMP | 3 (+ 1) days after the last dose of IMP | 5 (+ 1) days after the last dose of IMP | 7 (+ 2) days after the last dose of IMP | 10 (+ 2) days after the last dose of IMP |
| Visit | 16 | 17 | 18 | 19 | 20 | 21 |
| ENTRANCE/HISTORY | | | | | | |
| Concomitant medication(s) | Х | Х | Х | Х | Х | Х |
| EFFICACY | | | | | | |
| AISRS | | Х | | | Х | |
| SAFETY | | | | | | |
| Adverse events | Х | Х | Х | Х | Х | Х |
| Vital signs | | Х | | | Х | |
| SMWQ | Х | Х | Х | Х | Х | Х |
| Urine drug screen | | Х | | | Х | |
| Alcohol testing ^b | | X | | | Х | |
| C-SSRS | | X | | | X | |

^aFollow-up telephone calls will be conducted at 1, 3, and 5 days after the last dose of IMP, in-clinic visits on 2 and 7 days after the last dose of IMP, and a follow-up telephone call [or web, or other acceptable means of contact] 10 days after the last dose of IMP).

^bAlcohol testing may be conducted via a blood test or using a breathalyzer.

3.7.1 Schedule of Assessments

3.7.1.1 Screening and Baseline

3.7.1.1.1 Rollover Subjects

Screening for rollover subjects occurs simultaneously with baseline at the 7-day follow-up visit after Week 6/ET visit (Week 6) of double-blind phase 3 trial, (ie, Trial 405-201-00013 or Trial 405-201-00014) (Table 3.7-1) (Visit 1). Rollover subjects entering from double-blind phase 3 trial must sign the eICF for the open-label trial (ie, Trial 405-201-00015), before any procedures specific to Trial 405-201-00015 can be performed. Subjects will retain the same subject ID number assigned in Trial 405-201-00013 or Trial 405-201-00014. The following screening/baseline assessments may be conducted at the 7-day follow-up visits of Trial 405-201-00013 or Trial 405-201-00014 for the baseline visit: concomitant medications, AEs, vital signs, urine drug screen, alcohol testing, C-SSRS, and AISRS. The additional procedures to be performed for rollover subjects at baseline of the open-label trial are as follows:

- An assessment of all inclusion and exclusion criteria will be made to determine the subject's eligibility for the trial.
- Medical history from Trial 405-201-00013 or Trial 405-201-00014 will be retained, but will be updated if necessary.
- A qualified rater will administer the CGI-S.
- Subjects will complete the AIM-A.
- CC
- A physical examination including height measurements will be performed.
- A standard 12-lead ECG will be performed after the subject has been supine and at rest for at least 5 minutes. The ECG is to be completed before any blood is drawn.
- Blood samples will be collected for clinical laboratory tests, including hematology and serum chemistry (with glycosylated hemoglobin [HbA₁c], and thyroid-stimulating hormone [TSH and free thyroxine [T₄]). Blood will be drawn after a minimum 8-hour fast, if at all possible (see Section 3.7.4.2). See Table 3.4.3.1-1 for exclusions based on outcome of screening clinical laboratory tests. Vital sign and ECG assessments should be completed before any blood samples are collected.
- Blood samples will be drawn for human immunodeficiency virus (HIV) serology and the presence of hepatitis B surface antigen (HBsAg) and antibodies to hepatitis C virus (anti-HCV).
- A urine pregnancy test will be performed for all females of childbearing potential (FOCBP). If the urine pregnancy test is positive, the result should be confirmed with

Confidential - Proprietary Information

50

a serum pregnancy test. Subjects with a positive serum test result will be excluded from the trial.

- .AE recording will begin with the signing of the eICF for Trial 405-201-00015.
- Open-label centanafadine SR will be dispensed to the subject and subjects will be instructed to take their 2 doses at approximately the same time every day starting from Day 1 (day after baseline visit).

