3.3 Trial Population

3.3.1 Number of Subjects and Description of Population

A total of approximately 720 male and female subjects with a current diagnosis of ADHD are anticipated to be enrolled with the expectation that at least 300 subjects will achieve 6-month exposure and 100 subjects will achieve 52-week exposure.

The trial population will include approximately 560 completing rollover subjects from double-blind phase 3 trials (ie, Trial 405-201-00013 or Trial 405-201-00014) and approximately 145 de novo subjects between the ages of 18 and 55 years, inclusive, at the time of informed consent; de novo subjects must meet the DSM-5 criteria for ADHD including predominantly inattentive presentation, hyperactive presentation, or combined presentation) as confirmed by the ACDS Version 1.2. To confirm that ADHD is the primary diagnosis, the Mini International Neuropsychiatric Interview (MINI) will be used to identify and exclude other psychiatric conditions which would preclude enrollment.

Confidential - Proprietary Information

31

De novo subjects must washout of any prohibited medications prior to baseline (Table 4.1-2). Rollover subjects have already met the diagnostic criteria for ADHD (ie, DSM-5 criteria for ADHD as confirmed by the ACDS Version 1.2) as a part of their screening for the double-blind phase 3 trial (ie, Trial 405-201-00013 or Trial 405-201-00014) and have already been washed out of any prohibited medications prior to the start of the double-blind trial treatment phase, which will be confirmed prior to baseline of Trial 405-201-00015 via concomitant medication reporting and urine drug screening.

Subjects who roll over from Trial 405-201-00013 or Trial 405-201-00014 who turned 56 years old during that trial are also permitted to enroll in this trial.

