3.7.4.2 Clinical Laboratory Assessments

A central laboratory designated by the sponsor will be used for all laboratory testing required during the trial. The central laboratory should be used for all laboratory testing whenever possible (including unscheduled and follow-up, if needed). In cases where an immediate result is required for a particular laboratory test, the sample should be divided and sent to both a local laboratory and the designated central laboratory. Urine will be collected and blood will be drawn from each subject prior to treatment with the IMP. Subjects should be fasting for a minimum of 8 hours prior to the blood draws, if possible. If fasting blood samples are not feasible, non-fasting blood samples may be obtained initially for determining eligibility for the trial. A fasting blood sample is required at baseline prior to dosing. Clinical laboratory tests at other visits should be drawn fasting, if possible, but must be drawn after a minimum 8-hour fast at Week 52/ET. Vital sign measurements and ECG assessments should be completed before any blood samples are

Confidential - Proprietary Information

61

collected. See exclusion criteria (Section 3.4.3) for laboratory tests. For de novo subjects, if a fasting blood sample was obtained at the screening visit and less than 14 days have elapsed since the screening visit, clinical laboratory tests (hematology, serum chemistry, and urinalysis) do not need to be repeated at the baseline visit. The results of these tests must be reviewed by the investigator prior to initiation of the administration of the IMP. Additional urine and blood samples may be collected for further evaluation of safety as warranted by the investigator's judgment. Reports from the central laboratory will be retained electronically within the lab vendor's online portal and assessed by the investigator or qualified designee for clinical significance within eCRF.

Confidential - Proprietary Information

| Table 3.7.4.2-1 Clinical Laboratory Assessments | | | | |
|---|---|--|--|--|
| Hematology: | Serum Chemistry: | | | |
| Hematocrit | Albumin | | | |
| Hemoglobin | Alkaline phosphatase | | | |
| Mean corpuscular hemoglobin concentration | ALT | | | |
| Mean corpuscular hemoglobin | AST | | | |
| Mean corpuscular volume | Bicarbonate | | | |
| Platelet count | Bilirubin, total | | | |
| RBC count | Blood urea nitrogen | | | |
| WBC count with differential | Calcium | | | |
| | Cholesterol (total, HDL, LDL) | | | |

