7.1 Sample Size

The sample size is not based on statistical power considerations but on ICH/GCP requirements. The trial population will be derived from eligible subjects from the, double-blind phase 3 trial (ie, Trial 405-201-00013 or Trial 405-201-00014) and de novo subjects from selected sites. It is expected that approximately 560 completing rollover subjects from double-blind phase 3 trial (Trial 405-201-00013 or Trial 405-201-00014) and approximately 145 de novo subjects will be enrolled into this trial.

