## 9.2 Clinical Laboratory Tests

Summary statistics for mean and mean change from baseline in the routine clinical laboratory measurements, HbA1c, TSH, and PT/INR will be provided. Potentially clinically relevant results in laboratory tests will also be summarized.

Potentially clinically relevant laboratory measurement test results in the open-label treatment period will be identified, summarized, and listed. Criteria for identifying laboratory values of potential clinical relevance are provided in Appendix 2.

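### The rollover baseline visit list makes fasting optional where protocol Section 3.7.4.2 requires it, which exposes mean change from baseline in glucose and lipids

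*Protocol*

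**What the plan says.** Protocol Section 3.7.1.1.1 sets out the combined screening and baseline visit for rollover subjects. On the laboratory draw it says "Blood will be drawn after a minimum 8-hour fast, if at all possible (see Section 3.7.4.2". It names hematology and serum chemistry with HbA1c, TSH and free T4. It does not name PT/INR or urinalysis.

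Protocol Section 3.7.4.2 is stricter. It tolerates a non-fasting sample only initially, to settle eligibility, and then states "A fasting blood sample is required at baseline prior to dosing". For later visits it asks for fasting where possible, "but must be drawn after a minimum 8-hour fast at Week 52/ET". It also requires urine and blood from every subject before treatment.

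Table 3.7-1 (rollover schedule) marks two relevant rows at baseline. One is PT/INR. The other is "Clinical laboratory tests (hematology, serum chemistry [including HbA1c and TSH], and urinalysis", which is also marked at Week 38. Neither baseline mark carries the footnote that allows results to be brought over from the parent trial.

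On analysis, SAP 9.2 says "Summary statistics for mean and mean change from baseline in the routine clinical laboratory measurements, HbA1c, TSH, and PT/INR will be provided", and the table list in SAP 12 adds mean change in urinalysis (CT-10.3.3). SAP 7.1 takes as baseline the latest value before the first open-label dose, with no condition on fasting.

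**The concern.** De novo subjects meet the same soft fasting wording at screening (3.7.1.1.2.1), but a separate baseline visit with an unqualified fast follows (3.7.1.1.2.2). Rollover subjects have no such second visit. A site that follows the rollover list literally can take a fed sample, and that sample becomes the analysis baseline.

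The allowance for eligibility samples does not explain the soft wording. Exclusion criterion 10 in Table 3.4.3.1-1 rests rollover eligibility on the last parent-trial measurement, and Section 3.7.4.2 says baseline results arrive after dosing has begun.

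The trial has one arm, so no concurrent control absorbs a shift in baseline. A fed baseline set against a fasting Week 52/ET sample lowers the apparent change in any analyte that runs higher after food, such as glucose and triglycerides. SAP 9 presents rollover and de novo subjects in separate columns, so those columns could differ partly because their visit lists state different fasting rules.

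The unnamed tests matter less, but not nil. The urine protein and glucose flags in SAP Appendix 2 are defined as a rise of two or more units, which cannot be judged without a baseline.

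**Working it through.** **1. Fasting rules side by side**

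| Source | Visit | Fasting rule |
|---|---|---|
| Protocol 3.7.1.1.1 | Rollover baseline | Where possible |
| Protocol 3.7.4.2 | Baseline, all subjects | Required before dosing |
| Protocol 3.7.1.1.2.2 | De novo baseline | 8-hour minimum, unqualified |
| Protocol 3.7.4.2 and 3.7.1.2.9 | Week 52/ET | 8-hour minimum, mandatory |

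The first two rows conflict for the same draw. Table 3.7-1 footnote a puts the first dose on the day after the baseline visit, so the schedule offers no later fasting draw.

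**2. Tests named**

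PT/INR and urinalysis are marked at baseline in Table 3.7-1 and named in the de novo baseline list, but not in the rollover list. Urinalysis is part of the laboratory row marked at Week 38 in Tables 3.7-1 and 3.7-3, but Section 3.7.1.2.6 does not name it.

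**3. Share of subjects covered by the rollover list**

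Protocol 7.1 gives the components: "It is expected that approximately 560 completing rollover subjects from double-blind phase 3 trial" and "approximately 145 de novo subjects will be enrolled into this trial". Section 3.3.1 gives the total: "A total of approximately 720 male and female subjects with a current diagnosis of ADHD are anticipated to be enrolled".

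- Sum of components: 560 + 145 = 705. This is 15 below 720 (15/720 = 2.1%), close enough for approximate figures.
- Rollover share: 560/705 = 79.4%. On the stated total, 560/720 = 77.8%.
- Late rollovers follow the de novo path (SAP 3 and 6), and their number is not given. If 20, 50 or 100 of the 560 did so (assumed), the share would be 540/705 = 76.6%, 510/705 = 72.3% or 460/705 = 65.2%.

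**4. How many might be drawn non-fasting**

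The documents give no rate, so *f* below is an assumption, shown over a range. Let *D* be the fed-minus-fasting difference for an analyte, also not given. If de novo baselines and all Week 52/ET samples are fasting, and the enrolment mix holds among those analysed:

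- bias in mean change, rollover subjects = −*f* × *D*
- bias in mean change, all subjects = −(560/705) × *f* × *D*

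| Assumed *f* | Subjects (560 × *f*) | Share of 705 | Overall bias per 10 mg/dL of *D* |
|---|---|---|---|
| 5% | 28 | 4.0% | −0.4 mg/dL |
| 10% | 56 | 7.9% | −0.8 mg/dL |
| 20% | 112 | 15.9% | −1.6 mg/dL |
| 30% | 168 | 23.8% | −2.4 mg/dL |
| 50% | 280 | 39.7% | −4.0 mg/dL |

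The table shows how the effect scales. It does not predict its size. The mix at Week 52 may also differ from enrolment, since Section 3.3.1 expects only about 100 subjects to reach 52 weeks of exposure.

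**The case against.** The strongest reply is that the protocol already contains the right instruction. The rollover sentence sends the reader to Section 3.7.4.2, where the fast is required. The log entry for Administrative Change 1 in Appendix 5 also speaks of a fasting sample in rollover subjects, which suggests that this was the intent. That makes the conflict easy to resolve, but it does not remove it: the sentence at the point of use still permits what the cited section forbids.

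For PT/INR and urinalysis the reply is stronger. Section 3.7.1.1.1 cites Table 3.7-1, which schedules both. Its laboratory wording is not exhaustive, although it concerns blood and so cannot cover urine. Section 3.7.4.2 requires urine before treatment. A missing baseline would need a site to follow the list over the table.

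The outcome at risk is also limited. The primary endpoint is treatment-emergent adverse events. The relevance limits for glucose and lipids in SAP Appendix 2 are absolute, with a separate limit for non-fasting glucose, and HbA1c change is reported separately. A reader might infer that a rise on drug would go unseen, but these other summaries do not depend on a fasting baseline.

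A reader might also infer that 79% of subjects would lack a valid laboratory baseline. The documents do not support that. The figure is the share covered by the list, and a non-fasting draw leaves hematology, HbA1c, TSH and other chemistry with a usable baseline. Nor do they show that baselines would fall back to parent-trial values taken on double-blind drug: that needs a scheduled test to be skipped, and the parent schedules are not among these documents.

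**Conclusion.** The inconsistency on fasting is real, and the passages must be reconciled. It covers at most about 79% of expected subjects (560/705), fewer once late rollovers are counted on the de novo path, and the number actually drawn non-fasting is unknown.

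The results exposed are the descriptive mean changes in glucose and lipids, most clearly at Week 52/ET, where the fast is mandatory. The direction is downward for analytes that are higher after food. The size cannot be stated without a non-fasting rate and a fed-minus-fasting difference, and the documents give neither.

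The unnamed PT/INR and urinalysis are a secondary wording gap, because the schedule already requires both. The Week 38 urinalysis gap is post-baseline and does not bear on the baseline question.

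**What to change.** - **Protocol 3.7.1.1.1:** replace the optional fast with the baseline requirement of Section 3.7.4.2, and name PT/INR and urinalysis as in Table 3.7-1. Remind rollover candidates before the parent trial's 7-day follow-up visit to attend fasting.
- **Protocol 3.7.1.2.6 (Week 38):** reconcile the list with Tables 3.7-1 and 3.7-3 on urinalysis.
- **SAP 9.2:** add a summary of change in glucose and lipids for subjects fasting at both baseline and the visit concerned, or by fasting status, and keep the all-subject summary beside it. Confirm that fasting status is recorded for each sample. The relevance limits in SAP Appendix 2 already depend on it.

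No test is added. The cost is a reminder to subjects and smaller denominators for glucose and lipid change. Over the assumed range above, the restriction would remove between 28 and 280 of 705 subjects before other missing data, so the loss is not necessarily slight. That is why the all-subject summary should stay. If rollover enrolment has closed, the SAP change can still be made and addresses the bias by itself, provided fasting status was recorded.
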